In this study, volunteers were enrolled from the population with pre-dialysis CKD for the purpose of observing the frequency of CKD-PSI in the target population detected over time. The participants were assessed every 6 months via 1 annual clinic visit and 1 mid-year brief telephone follow-up for events that relate to CKD-PSI. The first 100 participants (Phase I) were provided with a standard medical alert accessory (bracelet or necklace) which is commonly used to alert doctors and other providers of a patient's disease state. In this case the medical alert accessory stated "Decreased Kidney Function. For My Care, Please Visit www.safekidneycare.org" Participants were asked to log onto a website using a unique 4-digit ID assigned by the PI to track their use of the website and to further improve the website. Since all information on the website was available to the public, participants are not required to use the ID to access the content of the website. The website did not collect or store patient health

information, except for the IP address which provides limited information on the location of the computer used to access the website (city, state, zip, and area code).

The volunteers in Phase I were tracked over time as to whether they accept and tolerated the medical alert bracelet/necklace and for their incidence of CKD-PSI. Enrollment continued after Phase I into Phase II (n = 250) with Phase II participants tracked on an identical study schedule for detection of CKD-PSI. All study procedures are the same for Phase II except for the medical alert accessory. The overall goal of this study will be to determine the frequency of CKD-PSI in the target population, the acceptability of an alert device (Phase I only) intended to increase the recognition of CKD, and the contribution of CKD-PSI to the high incidence of adverse outcomes in CKD.

Due to limited funding, beginning July 1, 2016, annual clinic visits stopped and study procedures were reduced to one, brief annual telephone follow-up to continue capture

- Self-reported safety events leading to hospitalizations/ER visits,
- Death and cause of death,
- Onset of end-stage renal disease requiring renal replacement therapy (dialysis and/or kidney transplant), and
- Updated contact information
- Frequency and severity of hypoglycemic episodes for participants with diabetes

Annual data collection of above-noted elements will continue for an additional 5 years through December 2021.

ID: VIEW4E02805CF7000

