Study Measurements: Participants in both Phase I and II underwent baseline and annual in-center visits for medical history and medication review, anthropometric measures, measurement of renal function (serum Cr for estimation of GFR); other laboratory measures, measures of physical function and health literacy, and other questionnaires. Additionally, they had a follow-up telephone call between annual visits to review medications, update contact information, assess for medical events and hospitalizations. Phase I participants also had an assessment of medical alert accessory acceptance and tolerance. The expected duration of study allows up to 4 annual clinic visits and up to 4 mid-year telephone follow-up visits through June 30, 2016. Beginning, July 1, 2016, annual clinic visits stop and will be replaced with just the annual telephone visit up to December 2021. The mid-year telephone follow-up will stop.

Primary outcomes: CKD-PSIs including medication errors (such as NSAIDs, improperly dosed meds), toxic exposures (such as contrast agents), and medical events (such as hyperkalemia or hypoglycemia); Secondary outcomes: including changing renal function, hospitalization, ESRD, and death. Phase I participants were followed for acceptance and tolerance of medical alert accessory.

- 3 * Describe the relevant prior experience and gaps in current knowledge. Describe any relevant preliminary data:
Refer to Protocol item 5. BACKGROUND

- 4 * Provide the scientific or scholarly background, rationale, and significance of the research and how it will add to existing knowledge:

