Every effort will be made to complete all visits within target range; however, we anticipate that some participants will miss some annual telephone visits due to unforeseen circumstances, such as illness or family events. At each encounter with the participant, we will attempt to collect all information on events that have occurred since the last encounter and complete data collection. Outlined below are the study procedures and questionnaires.

Participant and Designated Proxy Contact Information - participants will be asked to provide their preferred methods to be contacted, such as mailing address, telephone numbers, and email address. In addition, we will request that the participant provide the contact information of someone we can contact in case we have been unable to reach them, who can provide information to the participant's status, such as moved, ill, hospitalized, or deceased. This information is collected at each annual telephone follow-up visit.

Self-Reported Safety Events Questionnaire - this questionnaire tracks symptoms or medical problems that might be related to self- or medically-directed care and the frequency of hospitalizations.

Clarke Hypoglycemia Index_Questionnaire -Mod 12 adds one additional questionnaire, the Clarke Hypoglycemia Index_Questionnaire. This instrument will be administered beginning July 1, 2016 at the annual, telephone follow-up. Patients with diminished kidney function and diabetes are at risk for hypoglycemic episodes. The Clarke Hypoglycemia Index will provide information about the level of "unawareness" and ability to self-recover and avoid a patient safety event.

2 * Describe all procedures already being performed for diagnostic or treatment purposes (if not applicable to the study, enter "N/A"):

No procedures are being performed for diagnostic or treatment purposes.

3 * Describe the duration of an individual participant's participation in the study:

Mod 11 Changes to be initiated July 1, 2016: Length of participant may extend up to 10 years for those enrolled in 2011 and up to 7 years for the last participants enrolled in 2014.

4 * Describe the duration of the entire study:

Mod 11 Changes to be initiated July 1, 2016: Duration may extend to end of 2021.

5 * Describe any additional participant requirements:

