Generalized estimating equations (GEE) with log link function will be employed for examination of the relationship between incidence of CKD-PSIs and hospitalization. GEE will allow for joint modeling of the repeated measures and the incorporation of such a time-varying covariate based in the detection of a CKD-PSI. The effect of ever experiencing CKD-PSI during the study period on the frequency of hospitalization will be displayed by the rate ratio and its 95% confidence interval of hospitalization in PSI group versus non-PSI group.

Estimated GFR will be determined at baseline and at all annual follow-up visits. Since enrollment will be planned to ensure at least one follow-up visit per individual, it will be possible to generate slope estimates for change in renal function in all study participants. Measurement of serum creatinine will be done at a single laboratory to minimize variation in calibration across laboratories, and GFR will be estimated with the modified MDRD equation. Proper transformation will be performed as needed if the distribution of GFR values is skewed. Random effects models will be used to compare change in GFR between those with and without a CKD-PSI. To employ random effects models as a means to compare change in renal function between those participants with and without the incidence of a CKD-PSI and adjust for multiple covariates, the following assumptions will be made:

Each individual will have a separate slope β_i , with an independent intercept α_i , and an error term ϵ_i with mean 0 and a Normal distribution. The residual variance of each slope is assumed to be the same across all individual slopes and the distribution of β_i for participant time assigned to each group is assumed to be a Normal distribution with a mean of b_1 or b_2 corresponding to the two groups (without or with the bracelet/necklace). Similarly, the distribution of individual intercept α_i is assumed to be a Normal distribution with an equal variance across all individuals, and a mean of a_1 or a_2 corresponding to the two groups.

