The random effects model will allow for inclusion of both baseline and time-varying covariates which would include timing of the incidence of the CKD-PSI. In comparison of change in renal function across the two groups (CKD-PSI vs never CKD-PSI), we will test whether the mean slopes b_1 and b_2 are equal, and construct a 95% confidence interval for $d = b_2 - b_1$. For these analyses, we will employ PROC MIXED in SAS V9.1 (SAS Institute Inc., Cary, NC, USA), building on the research group's substantial prior experience using such models and examining changes in renal function.

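### The eGFR slope comparison does not say how or up to what date CKD-PSI exposure is assigned, so events recorded after the last eGFR could label slopes already measured

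*Combined protocol and SAP*

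**What the plan says.** **Outcome window.** Section 9.I.3 states: "Estimated GFR will be determined at baseline and at all annual follow-up visits". Under Justification, Objective, & Research Design (item 2, Study Measurements), "The expected duration of study allows up to 4 annual clinic visits and up to 4 mid-year telephone follow-up visits through June 30, 2016"; after that, "annual clinic visits stop and will be replaced with just the annual telephone visit up to December 2021". The lists of telephone-phase data in the Lay Summary and in Study Procedures (item 1) contain no creatinine.

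**Event window.** The telephone phase still collects "Self-reported safety events leading to hospitalizations/ER visits", together with deaths, onset of ESRD and, for participants with diabetes, hypoglycemic episodes. The Lay Summary adds: "Annual data collection of above-noted elements will continue for an additional 5 years through December 2021". Medication review and laboratory measures are no longer listed.

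**Slope groups.** Section 9.I.3 gives each individual one slope and tests equality of two mean slopes, introduced as "In comparison of change in renal function across the two groups (CKD-PSI vs never CKD-PSI". No date is given at which *never* is settled. The same section also describes slopes for the person-time allocated to each group, and says the model can carry the timing of the CKD-PSI as a time-varying covariate. Only hospitalization has an explicit rule: time before the first CKD-PSI is unexposed and time after it is exposed.

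**The concern.** Change in eGFR is one of the two key secondary outcomes in Section 9.I.3, and its link to CKD-PSIs is part of the study's overall goal. With one slope per person and an ever/never label, a participant whose first event falls in 2018 would belong to the CKD-PSI group, although every eGFR in that slope was measured by mid-2016. An event cannot have caused a decline that came before it.

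The same problem exists on a smaller scale within the clinic phase: an event in year 4 labels the eGFR values of years 1 to 3. If people whose GFR is falling are more likely to have a later CKD-PSI, steep slopes collect in the CKD-PSI group and d shows accelerated decline with no causal effect. The *never* group also shrinks as the event window lengthens.

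**Working it through.** **1. The plan's own figure.** Study Procedures (item 3) says participation may "extend up to 10 years for those enrolled in 2011 and up to 7 years for the last participants enrolled in 2014". 2021 - 2011 = 10 and 2021 - 2014 = 7, so this reproduces. No power or precision is given for the slope comparison.

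**2. Mismatch of windows.** Last possible eGFR: 30 June 2016. Last event collection: December 2021. The gap is 5.5 years, or more for a participant whose own last clinic visit was earlier.

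**3. Share whose group would change.** With annual incidence p, let L = -ln(1 - p) and let a be the years from the start of ascertainment (enrollment + 4 months, Section 9.I.3) to 30 June 2016.

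Share = exp(-L·a) × [1 - exp(-5.5·L)]

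The values of p lie within the 10% to 40% range of Table 4. Worked for enrollment at the start of 2013: a = 2016.5 - 2013 - 0.33 = 3.17.

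| p | L | event-free at June 2016 | first event in next 5.5 years | share changing group |
|---|---|---|---|---|
| 10% | 0.105 | 0.716 | 0.440 | 0.315 |
| 20% | 0.223 | 0.493 | 0.707 | 0.349 |
| 30% | 0.357 | 0.323 | 0.859 | 0.278 |

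Averaged over enrollment spread evenly across 2011 to 2014 (assumed), the shares are 31% / 35% / 29%. The *never* group falls from 72% / 50% / 34% (judged at June 2016) to 40% / 15% / 5% (judged at December 2021). These are upper-end figures, because they assume an unchanged event definition and the telephone set is narrower.

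**4. Effect on d when CKD-PSI has no effect.** Simulation of 350 participants, 600 runs per scenario, using a random-intercept, random-slope model with known variance components and a two-sided 5% test. Assumed, not in the documents: eGFR 40 (SD 12), slope -2 (SD 3) mL/min/yr, residual SD 4, no death, ESRD or dropout, and the same relationship between risk and GFR throughout follow-up.

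*No link between risk and GFR, or a link to entry GFR only:* with *never* judged to December 2021, d is -0.01 to 0.04 and the false-positive rate is 5% to 7%. There is no artefact.

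*Risk rising 1.1 / 1.3 / 1.5-fold per 10 mL/min lower current GFR, 20% annual incidence:*

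| Exposure rule | d (mL/min/yr) | False-positive rate |
|---|---|---|
| Ever/never to December 2021 | -0.80 / -2.15 / -2.85 | 29% / 93% / 99% |
| Ever/never to June 2016 | -0.22 / -0.66 / -0.97 | 9% / 37% / 68% |
| Ever/never to participant's last eGFR | -0.19 / -0.55 / -0.83 | 8% / 27% / 53% |
| Time-updated at first CKD-PSI | -0.09 / -0.28 / -0.42 | 5% / 9% / 15% |

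The last row estimates a change of slope after the first event, so it is not the same quantity as the between-group difference; the true value of both is zero here. Monte Carlo error is about 1 point near 5% and up to 2 points near 50%. Across 10% to 30% incidence, the first row ranges over -0.53 to -1.16, -1.53 to -2.72 and -2.28 to -3.26 for the three risk gradients.

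**5. What each change achieves.** The cut at the last eGFR removes 1 - 0.19/0.80 = 76%, 1 - 0.55/2.15 = 74% and 1 - 0.83/2.85 = 71% of d. With time-updating, d is smaller by 89%, 87% and 85%.

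**The case against.** The strongest reply is that the plan never says telephone-phase events define the slope groups. Section 9.I.3 is carried over from the protocol, relies on annual visits and does not mention the telephone phase. Nor do the documents say that telephone reports enter the CKD-PSI composite, although hypoglycemia is a named CKD-PSI example. If the timing of the CKD-PSI is used as a time-varying covariate, a 2018 event comes after every eGFR and changes nothing. The comparison is also secondary; the primary analysis of composite incidence is untouched.

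Much of this stands. A reader might infer that *never* is judged on events to December 2021. Study Procedures (item 4) says "Duration may extend to end of 2021", which makes that reading natural, but no sentence sets that cut-off. A reader might also infer that the extension by itself creates a slope difference. It does not: without a link between falling GFR and later events, d is about zero. The documents only propose to examine entry GFR against CKD-PSI incidence and note that diminished kidney function with diabetes carries hypoglycemia risk; neither quantifies a link with decline.

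What does not stand is that the time-varying wording settles the matter. It says what the model can include and does not define the groups. The person-time phrase sits in a sentence that labels the two groups by the medical alert accessory, so it is a weak guide. One slope per person, contrasted with *never*, still fits an ever/never split, and nothing would stop an analyst from using the later events.

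**Conclusion.** The point holds as an internal inconsistency with a conditional bias. The documents establish that study eGFR ends by 30 June 2016, that a narrower set of events is collected to December 2021, and that the slope contrast has no exposure cut-off and mixes ever/never with time-updated wording.

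Under an ever/never reading over the whole study, up to about 29% to 35% of participants would be classified by events after the last possible eGFR, given a constant 10% to 30% annual incidence. Bias in d then requires that falling GFR raises CKD-PSI risk. Its direction follows from that condition; its size depends on the assumed variances and risk gradients and should not be read as a forecast for this cohort.

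A reader might also conclude that a date cut-off alone cures the problem. That would be so only if risk were unrelated to GFR decline during the clinic phase. With one risk relationship throughout, the cut still leaves -0.19 to -0.83 mL/min/yr. The change is worth making before the slope analysis, but it does not threaten the primary result.

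**What to change.** In Section 9.I.3, replace the ever/never slope contrast with time-updated exposure. Suggested wording: *For the eGFR analysis, follow-up before a participant's first CKD-PSI counts as unexposed and follow-up after it as exposed, as in the hospitalization analysis. No event dated after the participant's last study eGFR defines exposure. The estimate of interest is the difference in slope between exposed and unexposed follow-up, with its 95% confidence interval. Because falling GFR may itself raise CKD-PSI risk, residual reverse causation may remain, and the result will be interpreted accordingly.*

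The cost is a few sentences and slightly more modelling work, with no new data. Telephone-phase events would not contribute to this comparison, but they cannot inform slopes that had already been measured. A change of slope estimated from a few annual values per person is likely to be imprecise, and the report should say so.
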